9.1 Completion and transfer of Case Report Forms (CRF)

Electronic Case Report Forms (CRFs) will be used in this study, which will be filled in by the investigator or designated participating staff members at the study sites. A separate case report form must be completed for each participant at each time point described in this protocol. Following review of the completed CRFs by the monitor, the first copy shall be transferred to the data administrator for data entry and management.

9.2 Data entry and modification

Questions regarding data submitted on the eCRFs will be sent to the investigators via a query form (QF); the data administrator shall modify, confirm, and enter the data according to the answers of the investigators, and issue a further QF if necessary.

9.3 Database locking

After completing the data review and confirming the correctness of the established database, the data administrators, principal investigators, sponsor, and monitors shall jointly review the data and complete the final definition and determination of the analysis population. The database will then be locked by the data administrator. The locked database or file may not be modified thereafter.

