The presence of proximal endoleaks, and amount of vessel wall apposition will be assessed via immediate post-deployment angiography to determine whether balloon dilatation is indicated. The brand type of balloon will be voluntarily selected by investigators. If the Hercules balloon is used, data pertaining to the Hercules balloon shall be recorded. The success rate of Hercules balloon technique and the rate of balloon rupture are used as efficacy and safety indexes for Hercules balloon device. All relevant data will be collected and analysed from time to time as the study progress.

4、 Study background

Abdominal Aortic Aneurysm (AAA) refers to the localized expansion of abdominal aorta exceeding 50% of the diameter of normal abdominal aorta, of which the main complication is rupture and bleeding, and once ruptured, the mortality is about 90%¹. The incidence rate of abdominal aortic aneurysm is growing year by year. Among the Asian population over 50 years old, the incidence rate of abdominal aortic aneurysm is 25.6%/100,000 in males and is 7.6%/100,000 in females; the incidence in men is about 3.5 times that of women². There is no AAA-related epidemiological data in China, but the detection rate of abdominal aortic aneurysm in China is also increasing year by year with the aging of the population, the application of various imaging techniques and the improvement of clinical understanding.

Currently, clinical surgical treatments of subrenal AAAs mainly include traditional open surgery and endovascular abdominal aortic aneurysm repair (EVAR). Traditional open surgery has the disadvantages of massive trauma and many types of complications. It is usually not considered suitable for patients with heart, lung, kidney, brain and other organ lesions. In 1991, Parodi first reported the application of EVAR in the treatment of AAA. Compared with traditional surgery, it can minimize the degree of surgical invasiveness and reduce the surgical risk, so that the frail and ill patients with AAA can access their therapies and achieve better curative effect. It has become the preferred treatment for most patients³⁻⁵.

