7.1.3 Measures to avoid and reduce bias

This study will be conducted in multiple centers in and outside of China at the same time. The Internet registration system will be used to register all participants. Clinicians in each study site will select those patients that meet the inclusion criteria to minimize any selection bias created by selection of ineligible patients. Standard operating practices will be adopted to reduce performance bias. Objective index data will be collected as much as possible; design and quality control measures will be strictly investigated, sufficient contact with participants will be maintained as far as possible to maximize the follow-up data obtained and to minimize patients and data lost to follow up during the life of the study. The imaging data obtained from follow-up investigations will be evaluated by blind film reading method as part of the study's data analysis stage. The relevant indicators such as device related adverse events and serious adverse events will be determined by an independent Clinical Event Committee and independent data management and statistical analysis will be utilized to avoid evaluation bias.

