8.1 Population

Full Analysis Set (FAS): set of subjects that are determined according to the "Intention To Treat" principle. Refers to all subjects who signed the Informed Consent Form, met all inclusion and exclusion criteria and were treated with Minos™ system.

Per protocol set (PPS): subset of the full analysis set. Refers to all subjects in whom Minos™ system has been successfully implanted, in whom the main evaluation indicators can be observed, and in whom no significant deviations from the study protocol have been observed.

Safety set (SS): refers to all subjects who have been enrolled and evaluated for safety.

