8.4 Criteria for termination of the study based on statistics

This study does not pre-establish interim analysis and the corresponding premature termination criteria, so this section is not applicable.

As a real-world study, the subjects will be followed up for 5 years. Periodic data statistical analysis is planned for 30 days, 6 months, 12 months, and 2-5 years post-procedure surgery. All statistical analyses shall be performed after the data have been collected, cleaned, and finally locked.

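### Section 9.3 lets the sponsor and principal investigators complete the definition and membership of the analysis sets at a pre-lock data review with nothing masking outcomes, although 8.1 already defines the sets

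*Protocol*

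**What the plan says.** Protocol 9.3 (Database locking) has four parties meet before lock: "the data administrators, principal investigators, sponsor, and monitors shall jointly review the data and complete the final definition and determination of the analysis population". Then: "The database will then be locked by the data administrator".

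Protocol 8.1 (Population) already defines three sets:
- The FAS takes consented subjects who satisfied every eligibility criterion and received the device.
- The PPS is the part of the FAS with a successful implant and observable main indicators, and "in whom no significant deviations from the study protocol have been observed".
- The safety set takes enrolled subjects evaluated for safety.

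Protocol 8.2 runs the effectiveness analysis in the FAS and the PPS.

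On timing, Protocol 8.4 says "Periodic data statistical analysis is planned for 30 days, 6 months, 12 months, and 2-5 years post-procedure surgery" and "All statistical analyses shall be performed after the data have been collected, cleaned, and finally locked". Protocol 3.2 adds: "All relevant data will be collected and analysed from time to time as the study progress".

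On safeguards, Protocol 7.1.3 provides blinded reading of follow-up images, an independent Clinical Event Committee, and says that "independent data management and statistical analysis will be utilized to avoid evaluation bias".

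**The concern.** A population review before lock normally applies rules that are already fixed. Section 9.3 gives the meeting two tasks: deciding who belongs to each set, and completing the definition of the sets. The second task is not needed if 8.1 stands. It hands rule-making to a group that includes the sponsor and the treating investigators, at a point where they are looking at the data.

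In a blinded randomised trial the meeting would not know treatment allocation, which limits what a selective exclusion can achieve. This study has no comparator, so that protection is absent. Removing a patient who failed shrinks the denominator and leaves the numerator alone, so the success rate can only rise. What is at stake is the credibility of the 12-month primary rate in both effectiveness sets.

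**Working it through.** **1. Does 9.3 reopen what 8.1 settles?** Yes. Section 8.1 defines FAS, PPS and safety set. Section 9.3 makes no reference to 8.1, does not confine the meeting to applying it, and assigns both definition and determination to the meeting.

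**2. What can the group see?** Section 9.3 says only that the data are reviewed. Section 9.1 has investigators or their staff complete the case report forms, so site-reported deaths, reinterventions and ruptures are available. Nothing in 9.3 restricts the review to listings without outcomes. Blinded film reading is placed in the data analysis stage (7.1.3), so central reads of endoleak and diameter may not exist yet.

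**3. Could earlier results be known?** Analyses are planned at 30 days, 6 months, 12 months and yearly after that (8.4), and as the study progresses (3.2). If each analysis has its own lock, earlier results may be known when the 12-month populations are settled. No text says that this group receives them, and none says that eligibility rulings carry forward.

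**4. Where does judgement enter membership?**
- *FAS*: all eligibility criteria must be met. The last listed contraindication (7.1.4) is a general unsuitability clause with no objective test.
- *PPS*: it turns on significant deviations. Section 8.1 does not tie that term to the major and minor classes in section 14, where the list of major deviations is expressly open.
- *An unsettled case*: 8.6 plans subgroups with neck length below 15 mm and neck angle above 60°. In 7.1.4 an angle above 60° is a contraindication, and the indication requires a neck length of at least 15 mm. Whether such patients can be in the FAS is unclear. The passages must be reconciled; meanwhile 9.3 leaves the question to the meeting.

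**5. How much could it matter?**

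Inputs: N = 200 (8.3, which gives no statistical derivation to reproduce); exact binomial 95% intervals (8.2); 12-month clinical success in the earlier study of 121/136 (section 4). Check: 121/136 = 88.97%, which agrees with the stated 89%.

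Assumptions: all 200 are evaluable, the 89% carries over to this endpoint, and *k* failures are removed. The documents give no value for *k*.

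Formula: rate = S / (200 − k), with Clopper-Pearson limits. At 89%, S = 0.89 × 200 = 178, leaving 22 failures.

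| Failures removed | Rate | 95% CI |
|---|---|---|
| 0 | 178/200 = 89.0% | 83.8 to 93.0 |
| 4 | 178/196 = 90.8% | 85.9 to 94.5 |
| 8 | 178/192 = 92.7% | 88.1 to 96.0 |

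Range over the assumed rate, for k = 5 and k = 10:

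| Assumed rate | k = 0 | k = 5 | k = 10 |
|---|---|---|---|
| 85% | 85.0% | 170/195 = 87.2% | 170/190 = 89.5% |
| 89% | 89.0% | 178/195 = 91.3% | 178/190 = 93.7% |
| 93% | 93.0% | 186/195 = 95.4% | 186/190 = 97.9% |

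For scale, the sampling half-width at 89% is 1.96 × √(0.89 × 0.11 / 200) = 4.3 points. Removing 4 failures shifts the rate by 1.8 points, and removing 8 shifts it by 3.7.

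**The case against.** The case on the other side has real force.

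- *A population review before lock is ordinary, and its details often sit in the SAP.* True, and no missing detail is criticised here. The point concerns what 9.3 states: that the meeting completes the definition.
- *A reader might infer that the group reviews unblinded outcomes with the results in hand.* The documents do not support that. Section 9.3 mentions neither unblinding nor outcomes, there is no allocation to unblind, blinded reads may come later, and the analysis for a given lock follows that lock (8.4, 9.4). What stands is that site-reported patient-level outcomes are available and not masked.
- *A reader might infer that 9.3 contradicts 7.1.3.* It does not. Independent data management and analysis can coexist with a joint review. But 7.1.3 is undercut when interested parties share the decision on the denominator. The blinded reads and the event committee protect how outcomes are assessed, not who is counted.
- *The route out of the FAS is narrow.* Under 8.1 as written, a treated, consented patient can leave only through an eligibility ruling. Section 14 makes enrolling an ineligible subject a major deviation, to be reported in the clinical summary report. This makes removals more visible but does not prevent them, does not require the outcome to be shown, and does not bind if the definition itself is changed.
- *The PPS already drops failed implants.* Correct. That effect comes from 8.1 and is not counted here.
- *There is no hypothesis test or performance goal, and a removal of 4 stays well inside the starting interval.* Also correct. No pass or fail decision turns on this; the effect is on a descriptive estimate.

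**Conclusion.** The point holds as a weakness in stated text. Section 9.3 lets the sponsor and principal investigators, with monitors and data administrators, finish defining the analysis sets and decide membership while site-reported outcomes are available to them. The 8.1 criteria leave enough judgement for outcome to influence exclusions.

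If 4 to 8 failures were removed from 200 at an assumed 89%, the 12-month rate would rise by 1.8 to 3.7 points. With 5 to 10 removed and assumed rates of 85% to 93%, the rise is about 2 to 5 points, similar to the sampling half-width. These are illustrations, because the number removed is assumed. The documents do not show that anyone would or will exclude failures. The remedy is nearly free, so the change should be made.

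**What to change.** 1. In 9.3 delete the reference to final definition and state that the review only applies the 8.1 definitions.
2. Decide eligibility and major or minor deviation status from listings without endpoint results, through the independent data management function promised in 7.1.3. The sponsor, monitors and investigators supply facts and do not decide. Section 7.1.3 names no group for this, so the protocol should say who performs it.
3. A wholly outcome-free listing cannot apply the PPS as written. Apply its implant and observability conditions mechanically, from recorded implant status and from whether the endpoint assessment is present or absent, not from its result.
4. Make each baseline eligibility ruling once and carry it unchanged through all periodic analyses.
5. List every treated subject left out of the FAS or PPS, with the reason and the primary outcome.

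Cost: rewording of 9.3 and one extra listing for a meeting that already takes place. The sponsor gives up discretion at lock. If no independent data management function is yet in place, assigning one is a further small task.

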9.4 Data processing

The locked database shall be provided to the statistical analysis personnel for statistical analysis.

10、 Feasibility Analysis

The Minos™ abdominal aorta stent graft and delivery system have undergone preclinical trial and testing and obtained medical device registration certificate in People's Republic of China, and CE certification in March 2019, September 2019, and 2017 respectively. It is therefore deemed to have met the relevant safety standards required by these certification methods.

The study sites participating in this study possess the necessary equipment and technical resources and have the required surgical experience in endovascular interventional therapy of aortic diseases to do so. The Principal Investigator at each site has sufficient clinical experience and academic status to undertake this role. Therefore, the study is expected to successfully achieve the objectives intended by the Sponsor.

11、 Quality Control

11.1 Subject enrollment

All subjects enrolled in the study will be registered in the online registration system.

11.2 Training

Before the initiation of the clinical trial, relevant personnel should be trained, and investigators of each centre will conduct a kick-off meeting to carry out training on the clinical protocol, the informed consent process, the use of devices, the completion of documents and other aspects of the study. During the study, the investigators and relevant personnel should be trained specifically in local standard of care practices.

11.3 Monitoring

During the clinical trial, the clinical research associate or other individual nominated by the sponsor will visit each study center in person or remotely according to the clinical monitoring plan, if one is to be used. The purpose of such visits will in part be to ensure that all the contents of the protocol are strictly adhered to.

11.4 Audit

During the study, including during patient enrollment and follow-up, professional auditors may be appointed to review the progress of the study, to ensure the accuracy, completeness, and timeliness of the data, as well as the compliance of the clinical process with relevant regulations.

11.5 Storage of original data

Original data, including the signed patient informed consent forms, relevant laboratory test reports, case records and other relevant patient-related records shall be stored at each study site, in accordance with local and national policies. Data pertaining to the study shall be stored for not less than 10 years after the termination of study.

12、 Ethical protection and informed consent

12.1 Ethical considerations

This study will follow the ethical guidelines set out in the Helsinki Declaration of the world medical assembly.

All parties involved in the study shall bear corresponding ethical responsibilities according to their respective responsibilities in the study. In case of any of the following circumstances, the investigator shall promptly report to the relevant department of the study site, and promptly notify the lead study unit and the reporting Ethics Committee:

1. Serious adverse events
2. Any revision of the documents approved by the ethics committee does not affect the rights, interests, safety and health of the subjects, and non-substantive changes not related to the purpose or end point of the clinical trial do not need to be reported in advance, but shall be notified in writing afterwards
3. Suspension, termination, or request for resumption of study after suspension
4. Circumstances affecting the rights and interests, safety, and health of subjects or the scientific basis of the study.

To protect the rights, interests, safety, and health of participants, should a deviation from the protocol take place in an emergency setting that cannot be reported at the time of occurrence, it shall be reported in writing as soon as possible in accordance with relevant regulations.

Pregnant women, the elderly, people with intellectual disabilities and patients in life-threatening situations should be avoided as subjects as far as possible; when it is necessary to select such participants, this should be done in accordance with the study's eligibility criteria and must comply with the relevant additional requirements put forward by the ethics committee.

Before subjects consent to participate in study, investigators shall fully explain the details of it to the patient, or his/her family, guardian, or legal representative. These details must include known, foreseeable risks and any potential adverse events. Following this, the subject or his/her legal representative should sign their name and date on the informed consent form, and the investigator who obtains the informed consent is also required to sign their name and date on the informed consent form.

The informed consent form shall indicate the date of issue and the date of any subsequent revised version. If the informed consent form is revised during the study, the revised informed consent form should be reviewed and

approved again by the Ethics Committee before it is executed, where necessary. After a revised informed consent form has been approved and sent to the study sites, all subjects who have not completed the study must sign a copy of the new version of the informed consent form.

All subjects have the right to withdraw from the study at any stage without any financial responsibility and without providing a reason for this decision.

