21. SIGNATURE OF STUDY SITES, INVESTIGATORS AND SPONSORS

.....23

Protocol Summary

1、 Objective

To evaluate the clinical outcomes of the Minos™ Abdominal Aortic Stent-Graft and Delivery System in the treatment of Abdominal Aortic Aneurysm in a real-world patient population through a post-market observational registry.

2、 Design

The study is designed as a prospective, multi-centre, post-market, real-world observational registry study. Continuous enrollment is to be conducted for all subjects treated with Minos™ Abdominal Aortic Stent-Graft and Delivery System who meet the inclusion criteria and who voluntarily consent to participate in the study. An enrollment duration period of 24 months is expected for this project and initially, 200 subjects (170 in China and at least 30 in Europe) are to be enrolled. Patient follow up – including CT imaging - will be undertaken in accordance with the usual standard of care at participating sites, and is expected to occur at 30 days, 6 months, 12 months and 2-5 years post-procedure.

3、 Endpoints

1. Primary endpoint

- Technical success rate at 12 months

2. Secondary endpoints

- Incidence of major adverse events at 30 days
- Immediate technical success rate
- Incidence of successful aneurysm treatment at 2-5 years
- All-cause mortality up to 5 years post-procedure
- Aortic aneurysm related mortality up to 5 years post-procedure
- Secondary intervention rates up to 5 years post-procedure
- Aneurysm diameter and variation in aneurysm diameter from 30 days to 5 years post-procedure
- Incidence of type I, III endoleaks from 30 days to 5 years post-procedure
- The incidence rate of stent migration, fracture, stenosis, occlusion and distortion from 30 days to 5 years post-procedure

3. Other endpoints: technical success rate of Hercules balloon and incidence of balloon rupture, where applicable.

4、 Population

Eligible patients will be enrolled according to the inclusion criteria and the exclusion criteria from multiple study sites.

Inclusion criteria

To be enrolled, patients must meet all the following criteria:

- Diagnosis of infrarenal abdominal aortic aneurysm
- Plan to treat with Minos™ Abdominal Aortic Stent-Graft and Delivery System;
- Voluntary participation and completion of Informed Consent Form, with willingness to participate in follow-up to 5 years post-procedure.

Exclusion criteria

- Subjects in whom use of the Minos™ Abdominal Aortic Stent-Graft and Delivery System is contraindicated.

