Indications:

- Abdominal Aortic Stent-Graft and Delivery System is indicated for the treatment of abdominal aortic aneurysms with a proximal neck length ≥ 15 mm.

Contraindications:

- Severe stenosis or calcification near the aneurysm, leading to difficulty in achieving apposition of vessel wall and stent graft.
- Difficult access due to severe stenosis or tortuosity in the iliac artery or femoral artery
- Subjects with ruptured aneurysm or acute aneurysm
- Subjects with an infectious aneurysm.
- Those who are allergic to contrast agents or unable to tolerate contrast agents due to renal insufficiency.
- Patients with severe coagulation disorder and/or high risk of postoperative hemorrhage.
- Aneurysmal neck angulation greater than 60°
- Patients with blood supply to vital organs originating from the aneurysmal sac.
- Patients with other comorbidities and whose life expectancy does not exceed one year
- Subjects with connective tissue diseases, such as Marfan syndrome
- Minors and pregnant women
- Subjects who are allergic to nitinol
- Subjects who are considered not suitable for treatment with stent graft.

5. Process

1. Case registration: The Internet registration system will be utilized to consecutively register all eligible patients who have been treated with Minos™ Abdominal Aortic Stent-Graft and Delivery System and voluntarily participated in the study.

2. Signing the Informed Consent Form

3. Case screening: Cases are selected according to inclusion and exclusion criteria

4. Case enrollment

5. Collecting the preoperative and intraoperative data

6. Postoperative follow-up: Imaging follow-up to be conducted in accordance with standard of care at participating sites, to include at 30 days, 6 months, 12 months and annually to 5 years after post-procedure. It is expected that all patients will complete this follow up schedule, but participants will not be excluded in the event that follow up is not completed.

7. Data analysis and summary: All relevant data will be collected and analysed from time to time as the study progress.

Flow chart of study:

Project	Visit1	Visit2	Visit3	Visit4	Visit5	Visit6	Visit (7-10)
Time points	Preoperative	Intraoperative	Discharge	30 days after surgery	6 months after surgery	12 months after surgery	2/3/4/5 years after surgery
Window period ³				±7d	±30d	±60d	±90d
Informed consent ¹	X						
Demographics	X						
Inclusion criteria	X						
Baseline / Disease history	X						
Physical examination	X						

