Pre-clinical testing was completed prior to CE marking and approval for use in the EU and a domestic pre-clinical investigation of the device in human patients was conducted following successful preclinical trials and testing. A total of 137 patients were enrolled, with an average age of 69.5 years. The 12-month clinical success rate was 89% (121 / 136), the rate of 30-day major adverse events was 1.5% (2/136), the 12-month all-cause

mortality was 7.4% (10 / 136), the aneurysm related mortality was 0.7% (1/136), and the safety and effectiveness have been verified. Therefore, the Minos™ Abdominal Aortic Stent-Graft and Delivery System has been authorized with the Registration Certificate for Medical Device of the People's Republic of China in March 2019, Certificate No.: GXZZ 20193130182. And was CE-Marked in September 2019, Certificate No.: M.2019.106.12584. On this basis, this post-market registry has been commenced to observe the medium and long-term clinical outcomes of Minos™ Abdominal Aortic Stent-Graft and Delivery System in the treatment of AAA in a real-world patient population.

References

- [1] 中华医学会外科学分会血管外科学组腹主动脉瘤诊断与治疗指南. 中国实用外科杂志, 2008, 28(11): 916-917.
- [2] YII M K. Epidemiology of abdominal aortic aneurysm in an Asian population. ANZ J Surg, 2003, 73(6): 393-395
- [4] Lederle F A , Freischlag JA , Kyriakides T C , et al. Long-term comparison of endovascular and open repair of abdominal aortic aneurysm. N Engl J Med, 2012, 367 (21): 1988-1997.
- [6] Barbanti M, Binder RK et al. Impact of low-profile sheaths on vascular complications during transfemoral transcatheter aortic valve replacement. EuroIntervention. 2013 Dec; 9(8):929-35.

5、 Product features, structural composition, working principle, mechanism of action and scope of study

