7.1 Design

7.1.1 Study objectives

The purpose of this study is to observe the clinical outcomes of Minos™ Abdominal Aortic Stent-Graft and Delivery System in the treatment of abdominal aortic aneurysm in a real-world patient population, to assess its effectiveness and the acceptability of the risks inherent in its use, and to identify any new or emerging risks.

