7.1.4 Selection of subjects

Inclusion criteria

To be enrolled, patients must meet all the following criteria:

- Diagnosis of infrarenal abdominal aortic aneurysm
- Plan to treat with Minos™ Abdominal Aortic Stent-Graft and Delivery System
- Voluntary participation and completion of Informed Consent Form, with willingness to participate in follow-up to 5 years post-procedure.

Exclusion criteria

- Subjects in whom use of the Minos™ Abdominal Aortic Stent-Graft and Delivery System is contraindicated.

Indications:

- Abdominal Aortic Stent-Graft and Delivery System is indicated for the treatment of abdominal aortic aneurysms with a proximal neck length ≥ 15 mm.
- **Contraindications:**
 - Severe stenosis or calcification near the aneurysm, leading to difficulty in achieving apposition of vessel wall and stent graft.
 - Difficult access due to severe stenosis or tortuosity in the iliac artery or femoral artery
 - Subjects with ruptured aneurysm or acute aneurysm
 - Subjects with an infectious aneurysm.
 - Those who are allergic to contrast agents or unable to tolerate contrast agents due to renal insufficiency.
 - Patients with severe coagulation disorder and/or high risk of postoperative hemorrhage.
 - Aneurysmal neck angulation greater than 60°
 - Patients with blood supply to vital organs originating from the aneurysmal sac.
 - Patients with other comorbidities and whose life expectancy does not exceed one year
 - Subjects with connective tissue diseases, such as Marfan syndrome
 - Minors and pregnant women
 - Subjects who are allergic to nitinol
 - Subjects who are considered not suitable for treatment with stent graft.

Criteria and procedures for termination of the study/treatment

- Should severe safety concerns arise, the study shall be suspended in time.
- If the therapeutic efficacy of the investigational device is found to be poor or ineffective such that it is of no clinical value, the study shall be suspended.
- The discovery of major errors in the clinical trial protocol or significant deviation from it, making it difficult to evaluate the safety and efficacy of the investigational product.
- The sponsor requests suspension (for the reason of funds, management, etc.)
- Revocation is issued by the approving authorities.

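### Section 12.1 tells sites to avoid elderly subjects where they can, which conflicts with consecutive enrolment of all eligible treated patients in a real-world registry

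*Protocol*

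**What the plan says.** Section 12.1 (Ethical considerations) lists groups that sites should try not to enrol: "Pregnant women, the elderly, people with intellectual disabilities and patients in life-threatening situations should be avoided as subjects as far as possible". The sentence goes on to a softer clause: "when it is necessary to select such participants, this should be done in accordance with the study's eligibility criteria", together with any further requirements of the ethics committee. The protocol gives no age at which a patient counts as elderly and no test of necessity.

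The enrolment rules read differently. The Protocol Summary (Design) and section 3.2 both state: "Continuous enrollment is to be conducted for all subjects treated with Minos™ Abdominal Aortic Stent-Graft and Delivery System who meet the inclusion criteria", subject to consent. Step 1 of the Process in the Protocol Summary says: "The Internet registration system will be utilized to consecutively register all eligible patients". Section 7.1.2 has the registration system take in all treated patients who consent, with investigators judging eligibility against the inclusion criteria.

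Section 7.1.4 restricts age only at the lower end, through the contraindication "Minors and pregnant women". Section 7.1.1 gives the aim as observing the device "in the treatment of abdominal aortic aneurysm in a real-world patient population". Section 4 reports on the earlier study of the same device: "A total of 137 patients were enrolled, with an average age of 69.5 years".

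**The concern.** The value of a single-arm registry with no hypothesis test rests on who is in it. Consecutive enrolment removes the site's discretion over which eligible patients are counted. Section 12.1 gives some of that discretion back, on a characteristic likely to be related to death, and does so in a disease of later life.

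Three other features leave the gap open:

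- The bias measures in section 7.1.3 address the selection of ineligible patients, not the omission of eligible ones.
- The major deviations named in section 14 include wrongful inclusion but not failure to enrol an eligible patient, although that list is stated not to be exhaustive.
- Note 1 to the flow chart says consent is ideally, so not always, obtained before the procedure. Some enrolment decisions could therefore be made with the procedural result known.

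At stake are the endpoints in which death counts: all-cause mortality to 5 years, and the 30-day major adverse events, which include death from any cause. If older patients are under-enrolled, these describe a younger group than the one receiving the device.

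**Working it through.** **No planned figure to reproduce.** The point is a conflict between statements. Section 8.3 says the sample size has no statistical basis, so there is no power or error rate to check.

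**Side by side.** Take an eligible 78-year-old who is treated with the device and willing to consent.

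| Source | What it implies for this patient |
|---|---|
| Protocol Summary (Design), 3.2 | Enrol |
| Protocol Summary (Process, step 1) | Register consecutively |
| 7.1.2 | Register |
| 7.1.4 | No age bar |
| 12.1 | Avoid where possible; select if necessary |

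Investigators are required to follow the protocol strictly (section 20.1). A site that enrols this patient can cite section 3.2, and a site that does not can cite section 12.1.

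**How much of the population might 12.1 touch?** The documents give a mean age of 69.5 years (section 4), but no standard deviation (SD) and no definition of elderly. Assume age is normal with SD 6 to 10 years. Then P(age ≥ c) = 1 − Φ((c − 69.5)/SD).

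| Cut-off c | SD 6 | SD 8 | SD 10 |
|---|---|---|---|
| 60 | 94.3% | 88.2% | 82.9% |
| 65 | 77.3% | 71.3% | 67.4% |
| 75 | 18.0% | 24.6% | 29.1% |

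A cut-off of 60 or 65 covers most such patients, and a cut-off of 75 covers roughly a fifth to three tenths.

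**What would partial avoidance do to the age mix?** If half the patients at or above c are not enrolled, mean age falls by 0.5·SD·φ(z)/(1 − 0.5·P), where z = (c − 69.5)/SD and P = P(age ≥ c). For c = 65 and SD 8: 0.5 × 8 × 0.341/(1 − 0.5 × 0.713) = 2.1 years, giving 67.4. Over SD 6 to 10, the mean falls from 69.5 to between 68.0 and 66.8 for c = 65, and to between 68.6 and 67.5 for c = 75.

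**What could it do to mortality?** This is an illustration only. Section 4 gives 12-month all-cause mortality of 10/136 = 7.4%. Assume 24% of patients are 75 or older and their mortality is r times that of the rest. Mortality under 75 is then 7.4/(0.76 + 0.24r):

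- r = 2: 7.4/1.24 = 6.0%
- r = 3: 7.4/1.48 = 5.0%

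These would be the registry rates if nobody aged 75 or older were enrolled. If half of them were enrolled, their share would be 0.12/0.88 = 0.136, and the rate would be the under-75 rate × (1 + 0.136(r − 1)):

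- r = 2: 5.97 × 1.136 = 6.8%
- r = 3: 5.00 × 1.273 = 6.4%

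The SD, the cut-off, the ratio and the degree of avoidance are all assumptions. The complete-avoidance figures are an upper bound on the shift for the cut-off and ratios chosen.

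**The case against.** The strongest reply is that section 12.1 is generic text on vulnerable subjects and was not written as a selection rule for this study. It names pregnant women, whom section 7.1.4 already excludes. It is phrased as advice, permits elderly subjects, and sends the reader back to eligibility criteria that have no upper age limit. In a registry of all treated patients, a site could reasonably treat the necessity condition as met. Every operative enrolment rule points towards inclusion, and section 4 itself presents endovascular repair as a way to reach frail and ill patients. If elderly meant 65 or over, following the sentence to the letter would remove most candidates, so sites may well ignore it.

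Much of this stands. A reader might infer that elderly patients are barred, or that sites face two commands that cannot both be obeyed. The wording supports neither: the instruction is discretionary and leaves room to enrol. A reader might also take 69.5 years as typical of the disease, but it comes from one 137-patient study of this device.

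What does not stand is that the softer clause cures the conflict. Enrolling any one patient in an observational registry of a marketed device is hard to call necessary. With both terms undefined, each site sets its own threshold, which is the discretion consecutive enrolment is meant to remove. Standard wording is still in force while it remains in the protocol.

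**Conclusion.** The conflict in the text is real, and nothing elsewhere in the protocol resolves it. The protocol sanctions a route to age-based selection in a registry whose enrolment rule and objective call for none. If sites used that route, mortality and 30-day event rates would probably look more favourable than among all patients treated, and the effect could differ between sites. The direction rests on the assumption that older patients die more often; the protocol reports no outcomes by age.

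The size cannot be derived from the documents. The 12-month mortality of 5.0% to 6.0% against 7.4% holds only under the assumed age share and mortality ratios with nobody aged 75 or older enrolled. It should not be read as an estimate.

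Two further inferences go too far. One is that the 12-month success rate would be inflated: death from any cause is not itself a component of the definition in section 7.1.5, and the documents do not link success to age. The other is that the registry is already biased or cannot be called real-world: nothing shows that any site has applied the sentence as an age filter. Confidence is high in the inconsistency, moderate in the direction of any bias, and low in its size.

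**What to change.** In section 12.1, delete the elderly from the list of subjects to be avoided and add:

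*Age alone is not a reason for non-enrolment. Every eligible patient treated with the device is offered participation consecutively. This section adds safeguards for vulnerable subjects and does not alter the eligibility criteria or consecutive enrolment.*

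Keep the rest of the sentence, including the additional ethics committee requirements, for the other groups. Those requirements should not be lost, because intellectual disability is not an exclusion criterion and section 12.3 covers only incapacitated subjects.

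The cost is a short protocol amendment with the ethics committee approval that section 12.2 requires, and a notice to sites. It needs no extra patients, visits or procedures, and changes neither eligibility nor treatment.
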